3. We aim to describe the prevalence of common mental health conditions (anxiety, depressive episodes, and recurrent depressive disorder) in people with IBD when compared to an age and gender matched cohort.
4. We aim to explore healthcare utilisation in individuals with IBD with and without common mental health problems.

Methods

Study design

We aim to perform a retrospective matched cohort study. We will match people with UC and CD, to people without IBD. A history of common mental health conditions was assessed at baseline (matching date) in both cohorts, and compared. Both cohorts will be followed-up (retrospectively) from the matching date for incident infections, and healthcare resource utilisation.

Data source

We aim to use the Royal College of General Practitioners (RCGP) Research and Surveillance Centre (RSC) database. This database contains the pseudonymised primary care records of the registered population all from a network of GP practices which provide a representative sample of the UK population.⁹ The RCGP RSC database contains complete data on all events and clinical entities coded in UK primary care. These include demographic information, clinical diagnoses, laboratory test results, primary care issued prescriptions, process of care codes (e.g. specialist referrals), and anthropometric measurements (e.g., body mass index; BMI), and are coded using the Read coding system.¹⁰

UK general practice records provide several advantages for this study type;^{11, 12} UK primary care is a registration-based system (a patient can only register with a single GP), records have been computerised since the 1990s, and pay-for-performance targets (introduced in 2004 through The Quality and Outcomes Framework; QOF) have resulted in consistent high-quality clinical data entry about chronic disease. Studies using the RCGP RSC data have been published across a range of chronic diseases.¹³⁻¹⁵ RCGP RSC practices get feedback on their data quality, including using a dashboard. A particular emphasis of this feedback is “episode typing” – designating cases first, new, or ongoing – which helps differentiate incidence from prevalence.¹⁶

Study population and outcome measures

All adults (aged ≥ 18) registered with a GP practice contributing to the RCGP RCS at the time of data extraction will be eligible for inclusion.

Definition of the IBD cohort

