The presence of common mental health conditions at baseline will be determined for the case and control cohorts. We will examine three groups of common mental illness as defined by the International Statistical Classification of Diseases and Related Health Problems 10th Revision (ICD10) classification;²⁰ depressive episodes (F32), recurrent depressive disorder (F33), and non-phobia related anxiety disorders (F41). These conditions are chosen as they represent the most common mental health conditions presenting to primary care.²¹ These conditions will be identified using algorithms validated in UK primary care.²² We selected the algorithms used here (Appendix 2) to optimise the positive predictive value. In brief, we will use a concurrent diagnosis and treatment code to identify acute episodes (depressive episodes and anxiety episodes) and for recurrent depression either a historical code for any depression and current treatment or a recurrent

depression specific diagnosis code (Appendix 2). As a secondary analysis we will also explore the prevalence of attention deficit hyperactivity disorder (ADHD) in the case and control cohorts.

Healthcare utilisation outcomes

The components of healthcare utilisation to be examined comprise; number and duration of primary care attendances, number of primary care prescriptions for antidepressant and anxiolytic medications, number of primary care prescriptions for medications used in IBD, recorded secondary care attendances, and issue of statements of fitness for work (also termed fit notes or sick notes).

Antidepressant medication classes to be examined comprise, selective serotonin reuptake inhibitors (SSRIs) and related medications (serotonin and norepinephrine reuptake inhibitors; SNRIs), tricyclic antidepressants (TCAs) and related medications (tetracyclic antidepressant TeCAs), and monoamine oxidase inhibitors (MOAIs). Anxiolytic medications to be examined comprise all benzodiazepines and other related medications indicated for use in anxiety states (Appendix 3). Medications used for the treatment of IBD to be examined will comprise; topical 5-aminosalicylic acid (5-ASA) medications, topical glucocorticoids, oral 5-ASA medications, oral glucocorticoids, non-biologic immunosuppressant medications (cyclosporine, azathioprine, mercaptopurine, methotrexate), and biologic therapies (Appendix 3).

Other baseline measures

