Socioeconomic status will be defined using the official national measure; the index of multiple deprivation (IMD).²³ This is calculated at the point of data extraction, using patient postcode, with the resultant scores stratified by deprivation quintile. Ethnicity will be extracted from the primary care record and grouped into major ethnic groups; white, black, Asian, mixed, and others.²⁴ BMI will be defined as the most recently recorded measurement prior to the study start date. Smoking status will be defined using the most recently recorded data prior to the study start date. Diagnosis codes will be used to define the presence of comorbidities at baseline; diabetes, hypertension, atrial fibrillation, angina, myocardial infarction, congestive heart failure, stroke, transient ischaemic attack, chronic kidney disease (stages 3–5), dementia, rheumatoid arthritis, chronic liver disease, asthma and chronic obstructive pulmonary disease (COPD).

Statistical Analyses

Comparison of the prevalence of mental health conditions

We will compare the prevalence of the three common mental health conditions in people with IBD and matched controls prior to the baseline date (January 1, 2015). We will stratify groups by age, and gender, and for those with IBD by condition (UC or CD) and duration of disease, and other important baseline factors. We will evaluate differences in baseline characteristics between the cohorts using the χ^2 test for categorical variables and the unpaired t-test for continuous data. Other statistical tests may be used if appropriate, depending on the data type and distribution.

Comparison of healthcare utilisation

We will compare the measures of healthcare utilisation between people with IBD and matched cohorts over a follow-up period. Follow-up will end at the earliest of; the study end-date (data extraction date), the date of patient transfer from an included practice, or date of death. All individuals contributing at least 1 day of follow-up will be included for analysis. We will stratify and compare healthcare utilisation in people with IBD by age and gender, condition (UC or CD), duration of disease, the presence of mental health conditions, and other important

confounders. All utilisation outcomes will be adjusted for the duration of follow-up and reported as event rates.

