Where sample size allows we will examine factors associated with increased healthcare utilisation. We will use regression analyses to assess potential associations between healthcare utilisation outcome measures and important patient and treatment factors.

Comparison of infections

Infection incidence rates will be calculated as the number of events divided by the total person-years of follow-up and expressed as the number per 1000 person-years. We will estimate the risk of infection in people with and without IBD using Cox proportional hazards models, and report estimated hazard ratios for associations with 95% confidence intervals. We will evaluate factors associated with an increased risk of infection. Factors assessed will include age, gender, socioeconomic status, household size (if available), comorbidities, and UC medications.

All statistical analyses will be performed in the R statistical package.

Ethical approval

Study approval will be requested from the Research Committee of the RCGP RSC. The study does not meet the requirements for formal ethics board review as defined using the NHS Health Research Authority research decision tool (<http://www.hra-decisiontools.org.uk/research/>).

Contributors

Research support for this project in several areas including data analysis, literature searching, and medication writing will be provided by Momentum Data. [name] and [name] of Momentum Data have contributed to the writing of this protocol and to the study design. Funding for these studies has been provided by Pfizer UK.

Scientific rigor and study registration

The team ethos at Momentum Data is to support the highest quality research, for patient benefit, with rigorous scientific standards. Publication bias remains an issue in observational studies. Therefore, if approval is granted the protocol will be registered as an observational study with ClinicalTrials.gov and made publicly available prior to the commencement of data analysis. Any protocol amendments will be published alongside this public record of the study and will be noted in any final publication with the rationale for the modification. Any changes will be assessed for the need for ethics approval and further RCGP RSC study approval; these will be sought if required.

References

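### Deprivation (IMD) is listed as a baseline measure but is taken from the postcode at data extraction, so people who change quintile during follow-up carry a post-baseline value

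*Combined protocol and SAP*

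**What the plan says.** The section headed "Other baseline measures" defines socioeconomic status by the IMD and states: "This is calculated at the point of data extraction, using patient postcode, with the resultant scores stratified by deprivation quintile". The neighbouring covariates are anchored differently. For BMI the rule is: "BMI will be defined as the most recently recorded measurement prior to the study start date". Smoking has the same restriction, and comorbidities are defined as present at baseline.

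The mental health comparison under Statistical Analyses fixes the time origin with the words "prior to the baseline date (January 1, 2015" (closing bracket omitted). Under Study design the plan says: "Both cohorts will be followed-up (retrospectively) from the matching date for incident infections, and healthcare resource utilisation". Under Comparison of healthcare utilisation, one of the events that ends follow-up is "the study end-date (data extraction date" (closing bracket omitted), so extraction and study end are the same date.

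Under Comparison of infections: "Factors assessed will include age, gender, socioeconomic status, household size (if available), comorbidities, and UC medications". For utilisation, socioeconomic status is not named; it could enter only through general references to confounders and patient factors. Nowhere does the plan mention a baseline postcode or an address history, or acknowledge the timing of IMD as a limitation.

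**The concern.** The infection outcome is time to first episode, analysed with Cox models. A covariate entered as fixed in such a model should be known at the start of follow-up. If IMD is read from the address at extraction, its value can post-date the infection it is meant to help explain.

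Two things follow for people who change quintile in between. If moving is unrelated to health, they are simply misclassified, which mostly dilutes the association between IMD and infection. If illness or loss of work during follow-up leads to a move to a more deprived area, the later quintile is partly a consequence of ill health, and part of the association runs backwards.

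The baseline comparison of the two cohorts has a related weakness: its IMD row would describe the end of the observation window, while the BMI, smoking and comorbidity rows describe the start.

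**Working it through.** The plan gives no figure on this point to reproduce. The check is a comparison of dates, followed by an illustration of size.

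**Timing rules side by side**

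| Covariate | Time of measurement in the plan |
|---|---|
| BMI | latest record before study start |
| Smoking | latest record before study start |
| Comorbidities | at baseline |
| IMD | at data extraction, which is the study end-date |

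IMD is the only one of these four tied to the end of the study rather than its start.

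**Length of the gap**

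- Baseline: 1 January 2015 (Statistical Analyses).
- Extraction date: not stated. The document date, 6 December 2018, is used as a stand-in.
- 1 January 2015 to 1 January 2018: 365 + 366 + 365 = 1,096 days. 1 January to 6 December 2018: 339 days. Total: 1,435 days.
- 1,435 / 365.25 = 3.93 years.

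**Share of people in a different quintile**

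The documents give no rate of address change, so these inputs are assumptions. With annual rate r and gap t = 3.93 years, the share who have moved is 1 − (1 − r)^t.

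- r = 2%: 1 − 0.98^3.93 = 7.6% moved. If half change quintile: 3.8%.
- r = 8%: 1 − 0.92^3.93 = 27.9% moved. If half change quintile: 14.0%.

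Wider assumptions show how far the result depends on them:

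- r = 2% and 30% of movers changing quintile: 7.6% × 0.3 = 2.3%.
- r = 10% and 70% of movers changing quintile: 1 − 0.90^3.93 = 33.9%, and 33.9% × 0.7 = 23.7%.

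These shares count all movers over the whole gap. Those who move and leave an included practice are censored at transfer, or excluded if the Study population rule (registered at extraction) is applied literally. The relevant group is movers still under follow-up, which is smaller. The reference list cites the 2015 edition of the deprivation index, so the area scores date from about baseline and the problem comes from people moving, not from areas being rescored.

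**The case against.** The best defence is that the sentence may only describe how a pseudonymised database processes postcodes. It does not say whether the postcode is the current or an earlier one, and nothing shows that address history is held. The plan discloses the timing, and a clearly labelled IMD row might be enough. Part of this stands: the remedy has to allow for historic postcodes being unavailable. But the natural reading is the postcode then on record, and disclosing when IMD is calculated does not make it a baseline value.

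A reader might infer several stronger points that the documents do not support:

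- **That the gap is at least 3.9 years.** The plan promises registration before data analysis begins, not before extraction, so the document date is not a lower bound for the extraction date.
- **That adjusting for late IMD strips out part of the IBD effect.** The plan names socioeconomic status as a factor assessed for infection risk; it does not say that the IBD hazard ratio is adjusted for it. The cohort is also prevalent, with IBD coded before study start, so even IMD on 1 January 2015 follows the disease. Only drift during follow-up can be blamed on this rule.
- **That the baseline table will show a spurious cohort difference.** That needs movement between quintiles to differ by IBD status, and the documents give no evidence that it does.
- **That the time of measurement varies with the outcome through deaths and transfers.** These are censoring events, not outcomes. The plan does not say which postcode is kept for people who leave, and the eligibility rule, read literally, excludes them.

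**Conclusion.** The timing inconsistency is real: a variable presented as baseline is calculated at the study end-date, and nothing else in the plan corrects this. It bears directly on the baseline comparison and on the infection risk-factor analysis; any effect on the utilisation analyses is only implied.

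The likely consequence is modest: dilution of, or some reverse causation in, the association between IMD and infection. The definitions of exposure and outcome are unaffected, and the main IBD-versus-control contrast need not be. The figure of roughly 4% to 14% misclassified rests on extraction near the document date, 2% to 8% of people moving each year and half of movers changing quintile. Other reasonable assumptions give about 2% to 24%, and censoring or exclusion of people who transfer out probably lowers all of these. No effect on a hazard ratio has been estimated. The point is worth correcting mainly because correction is cheap.

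**What to change.** Replace the IMD sentence with a rule such as: IMD quintile is assigned from the postcode or area code held on 1 January 2015 or, failing that, the last one recorded before that date.

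Where the database holds only the extraction-date postcode, say so and then:

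- label IMD in the baseline table as measured at extraction;
- do not interpret a difference in it as a baseline difference between the cohorts;
- report any model that includes IMD both with and without it.

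The cost is one sentence and, where address history exists, a different date in the extraction query. The downside is possibly more missing IMD where older postcodes are absent. The fallback needs no historic data and costs one extra run for each model that includes IMD.

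### The factor models for infection and utilisation name no method for correlation within GP practices; with default variance, intervals for factors that cluster by practice, chiefly deprivation, will be too narrow

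*Combined protocol and SAP*

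**What the plan says.** All references are to the combined protocol and SAP.

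- **Data source (Methods):** the database holds the "primary care records of the registered population all from a network of GP practices". Patients are therefore nested in practices.
- **Comparison of healthcare utilisation (Statistical Analyses):** the plan will "We will stratify and compare healthcare utilisation in people with IBD by age and gender, condition (UC or CD), duration of disease" and further characteristics. It adds "Where sample size allows we will examine factors associated with increased healthcare utilisation", followed by "We will use regression analyses to assess potential associations between healthcare utilisation outcome measures and important patient and treatment factors". No model family or variance estimator is given.
- **Comparison of infections (Statistical Analyses):** Cox proportional hazards models are named, and the analysts will "report estimated hazard ratios for associations with 95% confidence intervals". For the risk-factor part: "Factors assessed will include age, gender, socioeconomic status, household size (if available), comorbidities, and UC medications".
- **Other baseline measures:** socioeconomic status is the index of multiple deprivation, derived from each patient's postcode and grouped in quintiles.
- **Practice elsewhere:** the Abstract lists practice as a matching variable. Definition of the matched cohort requires only age and gender as a minimum. No section mentions clustering, a practice random effect or frailty, stratification by practice, generalised estimating equations or robust standard errors.

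**The concern.** Attendances, primary care prescriptions and fit notes are produced largely by the practice. Coded infection episodes depend on how each practice records; the Data source section itself describes data-quality feedback to practices on episode typing. Some correlation of outcomes within a practice is therefore plausible on the plan's own account. Patients of one practice also tend to live near one another, so postcode deprivation is likely to cluster by practice too.

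When outcome and factor both cluster in the same units, a standard error that assumes independent patients is too small. Chance differences between practices could then be reported as an effect of deprivation with false precision. The Lay Summary says the results should inform the allocation of healthcare resources, so the precision of a deprivation effect matters.

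Matching on practice, if done, would not cure this. Aims 2 and 4 ask about factors among people with IBD, and those comparisons are not between a case and its matched control.

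**Working it through.** The plan states no number of practices, patients per practice, event count or ICC, so there is no figure of its own to reproduce. Every input below is an assumption, apart from the two-sided 5% level implied by 95% intervals.

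**Formulas**

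- Design effect for a regression coefficient: DE = 1 + (m − 1) × ICC(outcome) × ICC(factor), where m is the number of IBD patients per practice.
- Correct interval width relative to the default: √DE.
- True error rate of a nominal 5% test: 2 × [1 − Φ(1.96/√DE)].

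**Two worked ends of the range**

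- Low: 1 + 9 × 0.01 × 0.3 = 1.027; √1.027 = 1.013; 1.96/1.013 = 1.93; error rate 5.3%.
- High: 1 + 89 × 0.05 × 0.6 = 3.67; √3.67 = 1.916; 1.96/1.916 = 1.02; error rate 31%. The default standard error is 1 − 1/1.916 = 48% too small.

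**Results across assumptions**

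| m | Outcome ICC | Factor ICC | DE | Correct/default width | True error rate |
|---|---|---|---|---|---|
| 10 | 0.01 | 0.3 | 1.03 | 1.01 | 5.3% |
| 30 | 0.05 | 0 | 1.00 | 1.00 | 5.0% |
| 30 | 0.05 | 0.05 | 1.07 | 1.04 | 5.8% |
| 30 | 0.02 | 0.3 | 1.17 | 1.08 | 7.0% |
| 30 | 0.05 | 0.3 | 1.44 | 1.20 | 10.2% |
| 30 | 0.05 | 0.5 | 1.73 | 1.31 | 13.6% |
| 90 | 0.05 | 0.6 | 3.67 | 1.92 | 31% |

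The factor ICC decides which results are affected. At zero there is no inflation whatever the outcome ICC. At 0.05, with m from 30 to 90 and outcome ICC from 0.02 to 0.05, DE runs only from 1 + 29 × 0.02 × 0.05 = 1.03 to 1 + 89 × 0.05 × 0.05 = 1.22, with error rates of 5.3% to 7.6%.

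**Simulation check** (linear model, 100 practices, m = 30, outcome ICC 0.05, 1,000 replicates). Coverage of nominal 95% intervals with the default standard error was 94.6%, 89.6% and 86.9% at factor ICC 0, 0.3 and 0.5. The formula gives 95.0%, 89.8% and 86.4%. With standard errors clustered on practice, coverage was 93.7%, 94.1% and 95.3%.

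**The case against.** The strongest reply is that the plan is silent rather than wrong. A reader might infer that it treats patients as independent and that its intervals are therefore too narrow. The documents do not support that: no sentence assumes independence, the utilisation regression is unspecified, and a mixed model or robust standard errors would fit the text. This stands, so the point is conditional on default variance being used. It still has force, because the named method for infections is a Cox model with no cluster or frailty term, and fitted that way it gives independence-based intervals.

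A second reply is that the effect may be negligible, since every input is assumed. This also stands: at the low end the intervals would be only about 1% wider.

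A third is that most listed factors (age, gender, comorbidities) are patient characteristics, and the documents give no reason to expect strong clustering of these by practice. A reader might infer that all the risk-factor results are compromised, or that deprivation is a practice-level variable. Neither follows. Weakly clustered factors are barely affected, and deprivation comes from patient postcode, so it can vary within a practice.

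Finally, the utilisation factor analysis is conditional on sample size and the aims are exploratory. That limits the consequences. However, the sample-size condition is attached only to utilisation; the evaluation of infection risk factors is an unconditional commitment.

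**Conclusion.** The concern holds in conditional form. The plan names no method for within-practice correlation in the infection and utilisation factor models. If they are run with default variance, intervals for factors that cluster by practice will be too narrow, with deprivation the main named candidate. Under the assumed inputs the design effect lies between about 1.03 and about 3.7, and the true error rate of a 5% test between about 5.3% and about 31%. The documents cannot place the study within that range.

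This is a matter of error bars on factors that cluster. It does not invalidate the study, and it is separate from any confounding of the comparison between IBD and matched controls.

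**What to change.** In Statistical Analyses, under both Comparison of healthcare utilisation and Comparison of infections, state that the factor models use robust (sandwich) variance clustered on GP practice and that the reported 95% confidence intervals are those. Report the number of practices, so that readers can judge how well the clustered variance is estimated.

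The cost is small. For the Cox models in R it is a clustering term in the model call; the utilisation regressions need the equivalent clustered variance. Practice membership should already be available, since follow-up ends when a patient transfers out of an included practice. The downside is wider intervals for factors that cluster by practice.

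A practice frailty or random effect should not be offered as an interchangeable option. It changes the estimand to a within-practice effect, so it belongs in a sensitivity analysis at most.

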Ulcerative colitis (UC) and Crohn's disease (CD) are chronic inflammatory conditions collectively termed inflammatory bowel disease (IBD).¹ In both conditions there is a spectrum of disease ranging from a quiescent state with few or no symptoms to potentially fatal disease. Both conditions commonly require extensive medical intervention over many decades of disease and may also require substantial surgical treatment.^{2, 3} With the global burden of IBD rising, calls have been made for improved treatment options,⁴ and these been met with the development of a range of biologic therapies.¹

Current treatment strategies for UC focus on the use of immune modulating medications. Whilst frequently effective for disease control, these treatments have the potential to increase the risk of common infections,^{5, 6} which includes both common and atypical pathogens.⁶ An understanding of the infection risk in a community-based population with UC is therefore important. However, the existing literature on infection rates in people with UC has focused almost exclusively on secondary care populations. It therefore remains unclear what the total burden of infectious disease is in a population-based cohort with UC and how this compares to those without UC.

Despite increasing treatment options, quality of life is significantly reduced in people with IBD⁷ and the prevalence of mental health disorders has been reported to be higher in children with IBD.⁸ However the magnitude of any potential association between IBD and mental illness in adults has not yet been fully explored.

Given the prolonged course of medical treatment in IBD, it is important for payers to have a good understanding of the total healthcare utilisation of people with IBD. Again, in this area, existing studies have focussed on secondary care based cohorts. Little is known about healthcare resource utilisation in primary care, in people with IBD, in the UK.

Aims

1. We aim to describe the incidence of common infections in a population of individuals with IBD, compared to a matched control population without IBD. We will explore all common infections and also focus on viral and gastrointestinal infections.
2. We will explore how incidence of infection varies by age, and other factors associated with risk of infection in IBD including medication use.

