All individuals with one or more diagnostic codes for UC or CD prior to the study start date were eligible for inclusion in the IBD cohort. The use of diagnostic codes to identify IBD from UK primary care records has been validated and shown to be accurate and to correctly differentiate between UC and CD.^{17, 18} The Read codes used to identify UC and CD were based on the codes list used by Abrahami et al.,¹⁸ and mapped to both Read code versions used within the RCGP RSC network (Appendix 1). The use of diagnostic codes to identify IBD has also been shown to have good validity in US claims databases.¹⁹

Definition of the matched cohort

The matched unexposed cohort will be identified by matching individuals with IBD to people without IBD. Matching will be performed on age and gender as a minimum. Follow-up for each matched individual will begin at the same baseline date as those with IBD.

Infections outcomes

Infections outcomes will comprise:

1. The time to first recorded presentation with a new episode of any common infection during the study period; a composite of upper respiratory tract infections, pneumonia, bronchitis, influenza-like illness, skin infections, genital infections, urinary tract infections and gastrointestinal infections.
2. The time to first recorded presentation with a new episode of any viral infection.
3. The time to first recorded presentation with a new episode of any episode of gastrointestinal infection.

The Read codes used to identify infections will be adapted from the validated indicators used in routine surveillance by the RCGP RSC. The chosen infections in the composite infections outcomes were selected principally as they represent the majority of the primary care adult infectious disease burden, and include a mixture of viral, bacterial and fungal infections. First or new episodes of an infection are coded accordingly in the database, enabling differentiation from chronic infections or follow-up visits for the same episode. If available, we will also explore type and pathogens contributing to the incident infections.

Mental health outcomes

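### Does dividing infection episodes by total person-years of follow-up make the planned incidence rates too low?

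*Combined protocol and SAP*

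**What the plan says.** The section Infections outcomes defines three endpoints, each as a time to a first new episode. For the composite it reads "The time to first recorded presentation with a new episode of any common infection during the study period"; the viral and gastrointestinal outcomes follow the same pattern. Each person therefore has at most one event per outcome.

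Under Statistical Analyses, Comparison of infections, the plan says "Infection incidence rates will be calculated as the number of events divided by the total person-years of follow-up", expressed per 1000 person-years. The next sentence plans Cox proportional hazards models with hazard ratios and 95% confidence intervals.

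The infection section does not say when person-time ends. The one end rule is under Comparison of healthcare utilisation: "Follow-up will end at the earliest of; the study end-date (data extraction date), the date of patient transfer from an included practice", or death. That subsection closes with "All utilisation outcomes will be adjusted for the duration of follow-up and reported as event rates".

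Two other passages set a common start. Study design says "Both cohorts will be followed-up (retrospectively) from the matching date for incident infections, and healthcare resource utilisation", and Definition of the matched cohort says "Follow-up for each matched individual will begin at the same baseline date as those with IBD".

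**The concern.** Read together, these passages can be taken to mean first episodes in the numerator and all follow-up in the denominator. Someone infected early would then keep adding person-years for an event that they can no longer have. The rate would fall below the true first-episode rate, and would fall furthest in the group with more infections if both groups are followed for similar lengths of time.

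The rates are results in their own right. Aim 1 reads "We aim to describe the incidence of common infections in a population of individuals with IBD, compared to a matched control population without IBD", and Aim 2 reads "We will explore how incidence of infection varies by age, and other factors associated with risk of infection in IBD including medication use". Understated rates would blunt crude comparisons between IBD and control groups, and would not agree with the hazard ratios printed beside them. The composite was chosen to cover most of the adult infection burden in primary care, so it could be frequent enough for this to show.

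**Working it through.** The plan gives no infection rate, event count or expected hazard ratio, so there is no figure to reproduce. The check asks how large the error would be under the unfavourable reading, and whether the text leads an analyst there.

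**Size under the unfavourable reading.** Assume equal follow-up T and a constant hazard μ. The proportion with a first episode is P = 1 − exp(−μT).

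- Rate on time at risk: μ = −ln(1−P)/T.
- First episodes over full follow-up: P/T.
- Shortfall: 1 − P/(−ln(1−P)).
- Ratio of full-follow-up rates at true hazard ratio h and control proportion P₀: (1 − (1−P₀)^h)/P₀.

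Example at P = 50%: 1 − 0.5/0.693 = 27.9%. At h = 1.5: (1 − 0.5^1.5)/0.5 = 0.646/0.5 = 1.29.

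| P (assumed) | Rate too low by | Ratio if true HR 1.5 | Ratio if true HR 1.2 |
|---|---|---|---|
| 5% | 2.5% | 1.48 | 1.19 |
| 10% | 5.1% | 1.46 | 1.19 |
| 25% | 13.1% | 1.40 | 1.17 |
| 50% | 27.9% | 1.29 | 1.13 |

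The shape of the hazard matters moderately. At P = 50%, a Weibull hazard with shape 1.5 gives 22.6% and with shape 0.7 gives 32.3%.

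**Does the contrast always shrink?** Add loss at yearly rate c. The full-follow-up rate becomes [μ/(μ+c) × (1 − exp(−(μ+c)T))] / [(1 − exp(−cT))/c]. Take T = 3.93 years (1 January 2015 to the document date of 6 December 2018, because no extraction date is given), an assumed μ of 200 per 1000 person-years in both groups, and assumed loss of 5% a year in controls and 20% in IBD.

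- Controls: 0.5005/3.568 = 140.3 per 1000.
- IBD: 0.3962/2.722 = 145.6 per 1000.
- Ratio: 145.6/140.3 = 1.04, where the truth is 1.00.

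Shrinkage therefore depends on similar follow-up in the two cohorts.

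**Which readings are affected?** A simulation used 20,000 people per group, a control rate of 200 per 1000 person-years, a true hazard ratio of 1.2, 8% yearly loss and T = 3.93, all assumed.

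| Rate per 1000 person-years | Control | IBD |
|---|---|---|
| First episodes over time to first episode | 200 | 242 |
| First episodes over total follow-up | 141 | 160 |
| All new episodes over total follow-up | 199 | 239 |

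The Cox hazard ratio was 1.21. Of the three rates, only the middle one is biased.

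**Does the text lead there?** The middle row needs the utilisation end rule to be carried into the infection section. In its own place the rule is right: attendances and prescriptions recur, so time after an infection belongs in their denominator. The shared-follow-up sentence in Study design fixes a start, not an end. The infection outcomes are times to first episode, and the Cox model needs exactly that time for each person. To get the middle row, an analyst would have to build that variable for the model and then use a different one for the rate beside it.

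**The case for a change.** The strongest case for a change is that the wording admits three different rates and the plan does not choose. The word total leans towards the biased one, and Study design describes one follow-up for infections and utilisation together. Where the plan wants counts, it says so in the utilisation outcomes; no all-episode infection outcome is defined, so first episodes are the natural numerator. The protocol is to be registered publicly before analysis, and one sentence would settle the matter without new data.

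Much of this stands. The text is incomplete, the direction of the possible error is right under similar follow-up, and for a frequent composite the error would not be trivial. It does not show a wrong analysis. For a time-to-event outcome, person-years of follow-up is commonly understood as time to event or censoring. The plan does not restrict events to first ones, and it notes that new episodes are coded separately from chronic infections and repeat visits for the same episode, so the all-episode reading is available and unbiased, though it fits the defined outcomes less well. No rate ratio or rate difference is planned; only an informal comparison of crude rates could be distorted.

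**Conclusion.** No change is needed. The infection section leaves out two details: whether events means first or all new episodes, and when infection person-time ends. The outcome definitions and the adjacent Cox model supply a sound answer: first episodes over time to first episode, transfer, death or extraction. Writing that down would record a definition, not correct a stated error.

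If an analyst did divide first episodes by full follow-up, crude rates would be 2.5% low at P = 5% and 27.9% low at P = 50%, assuming a constant hazard and equal follow-up. A true hazard ratio of 1.5 would appear as a crude rate ratio of 1.48 and 1.29 respectively. The documents give nothing from which to choose P, and the direction of the effect on contrasts also depends on similar loss in the two cohorts. The planned hazard ratios are unaffected throughout.
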